## 5.2 Determination of Sample Size

The data analysis from the single center study by Zinman et al (24) indicated that the SD for change from Baseline to Day 14 in QMG score is in the range of 2.74 – 3.48. To be

conservative considering multi-national study, the SD of 6.0 for QMG score change from Baseline to Day 14 is assumed, with 2-sided test, 33 subjects are needed to have 90% power to detect a clinically significant improvement of 3.5 in mean change in QMG (24). Fifty subjects are planned to be enrolled for the study.

## 6 ADMINISTRATIVE

### 6.1 Investigators, Other Study Personnel and External Committees

Information regarding additional key personnel involved in the conduct of the study, including names and contact details of participating Investigators, monitors, clinical laboratories, technical departments and/or institutions, as well as information on members of additional study committees, will be found in the study files of the Sponsor and at the Investigator sites within the Study Reference Manual/file.

Investigators and staff will receive training via an Investigators meeting, site initiation visit or other appropriate individual site training session(s).

### 6.2 Data Quality

Monitoring and auditing procedures defined/agreed by the Sponsor will be followed, in order to comply with ICH GCP guidelines. Each center will be visited at regular intervals by a monitor to ensure compliance with the study protocol, ICH GCP and legal aspects. The on-site verification of the eCRF for completeness and clarity will include cross checking with source documents and clarification of administrative matters. Query verification of data will be described in the Data Management Plan.

### 6.3 Documentation

The study data will be recorded and kept current in the eCRF by the site study personnel directly responsible for the information. Entries made in the eCRF must be verifiable against source documents or have been directly entered into the eCRF, in which case the entry in the eCRF will be considered the source data.

The data in the eCRF will be monitored at the site by Grifols Therapeutics Inc. representatives at regular intervals and reviewed for completeness and compared with the source documents. Examples of source documents include individual subject medical records, which are separate from the eCRFs.

All AEs and SAEs must be recorded. All SAEs must be recorded on the SAE form. The SAE form must be kept in site records with a copy provided to the designated person as detailed in [Section 4.4.9](#).

#### 6.3.1 Record Retention

At study completion, all study data will be transferred to Grifols Therapeutics Inc. according to ICH GCP guidelines, local laws, regulations and Grifols Therapeutics Inc. requirements.

The study file and all source data should be retained until notification is given by the Sponsor for destruction.

An Investigator is required by ICH GCP guidelines to retain the study files. If an Investigator moves, withdraws from an investigation or retires, the responsibility for maintaining the records may be transferred to another person (e.g., other Investigator). Grifols Therapeutics Inc. must be notified in writing of the person responsible for record retention and the notification will be retained in the Sponsor study file and the Investigator site file.

### 6.3.2 Access to Information for Monitoring

The data will be recorded and kept current in eCRFs by the study site personnel directly responsible for the information and reviewed for completeness by the monitor. Grifols Therapeutics Inc. personnel or designee can review the records.

In accordance with ICH GCP guidelines, the monitor must have direct access to the Investigator's source documentation in order to verify the data recorded in the eCRFs for consistency and to verify adherence to the protocol and the completeness, consistency and accuracy of data entered. "Source documentation" includes individual subject files, separate from the eCRFs, which should be maintained and include visit dates, laboratory results, concomitant treatment, vital signs, medical history, examinations, AEs, IP dispensing logs and other notes as appropriate. The Investigator agrees to cooperate with the monitor to ensure that any problems noted during the course of these monitoring visits are resolved.

### 6.3.3 Access to Information for Audits or Inspections

Representatives of regulatory authorities or of Grifols Therapeutics Inc. may conduct audits or inspections of the Investigator study site. If the Investigator is notified of an audit or inspection by a regulatory authority, the Investigator agrees to notify the Grifols Therapeutics Inc. Medical Monitor immediately. The Investigator agrees to provide to representatives of a Regulatory Agency or Grifols Therapeutics Inc. access to records, facilities and personnel for the effective conduct of an audit or inspection.

## 7 ETHICAL AND LEGAL ASPECTS

### 7.1 Institutional Review Board/Ethics Committee

Documented approval from appropriate IRBs/ECs will be obtained for all participating centers/countries prior to study start, according to ICH GCP guidelines, local laws, regulations and organizations. When necessary, an extension, amendment or renewal of the IRBs/ECs approval must be obtained and also forwarded to the Sponsor. The IRBs/ECs must supply to the Sponsor, upon request, a list of the IRBs/ECs members involved in the vote and a statement to confirm that the IRB/EC is organized and operates according to ICH GCP guidelines and applicable laws and regulations.

## **7.2 Ethical Conduct of the Study**

The procedures set out in this protocol, pertaining to the conduct, evaluation and documentation of this study, are designed to ensure that the Sponsor and Investigator abide by ICH GCP guidelines. The study will also be carried out in keeping with applicable local law(s) and regulation(s). This may include an audit by the Sponsor representatives and/or an inspection by Regulatory Authority representatives at any time. The Investigator must agree to the audit or inspection of study-related records by the Sponsor representatives and/or Regulatory Authority representatives and must allow direct access to source documents to the Sponsor and/or Regulatory Authority representatives.

Modifications to the study protocol will not be implemented by either the Sponsor or the Investigator without agreement by both parties. However, the Investigator may implement a deviation from, or a change to, the protocol to eliminate an immediate hazard(s) to the study subjects without prior IRB/EC/Sponsor approval/favorable opinion. As soon as possible, the implemented deviation or change, the reasons for it and if appropriate the proposed protocol amendment should be submitted to the IRB/EC/Sponsor. Any deviations from the protocol must be fully explained and documented by the Investigator.

## **7.3 Regulatory Authority Approvals/Authorizations**

Regulatory Authority approvals/authorizations/notifications, where required, must be in place and fully documented prior to study start. Study information including contact information for Investigator sites responsible for conducting the study will be posted on a publicly accessible clinical registry(ies) as required by local law.

## **7.4 Subject Information and Informed Consent Form**

Subject information and ICF will be provided to Investigator sites. Prior to the beginning of the study, the Investigator must have the IRB/EC written approval/favorable opinion of the written ICF and any other written information to be provided to subjects. The written approval of the IRB/EC together with the approved subject information/ICF must be filed in the study files and a copy of the documents must also be provided to Sponsor by the Investigator site.

Written ICF must be obtained before any study specific procedure takes place. Considering the nature of this emergency indication, potential subjects may receive information regarding the study in advance of experiencing an MG exacerbation. However, when experiencing an MG exacerbation, the subject or legally authorized representative will be informed again and will sign the written ICF prior to any study specific procedure being conducted.

If applicable, a legally authorized representative may provide informed consent on behalf of the subject. Participation in the study and date of ICF given by the subject should be documented appropriately in the subject's files. A signed copy of the subject ICF will be provided to the subject or subject's authorized representative.

## 7.5 Insurance

All subjects participating in the study will have insurance coverage by the Sponsor, which is in line with applicable laws and/or regulations.

## 7.6 Confidentiality

All records identifying the subject will be kept confidential and, to the extent permitted by the applicable laws and/or regulations, will not be made publicly available.

Subject names will not be supplied to the Sponsor. Only the subject number will be recorded in the eCRF, and if the subject's name appears on any other document (eg, pathologist report), it must be obliterated before a copy of the document is supplied to the Sponsor. Study findings stored on a computer will be stored in accordance with local data protection laws. Subjects will be informed in writing that representatives of the sponsor, IRB/EC or Regulatory Authorities may inspect their medical records to verify the information collected and that all personal information made available for an audit or inspection will be handled in strictest confidence and in accordance with local data protection laws.

If the results of the study are published, the subject's identity will remain confidential.

The Investigator will maintain a list to enable subjects' records to be identified.

## 8 USE OF DATA AND PUBLICATION

Institution and the Investigator agree that the first publication shall be made in conjunction with the presentation of a joint, multi-center publication of the study results from all appropriate sites. If such a multi-center publication is not submitted within twelve (12) months after conclusion of the study at all sites or after Grifols confirms there will be no joint, multi-center publication, then institution and/or Investigator shall have the right, at their discretion, to publish, either in writing or orally, the results of the study performed under the protocol, subject to the conditions outlined below:

- The results of the study will be reported in the publicly accessible registry(ies).
- Institution and/or Investigator shall furnish Grifols with a copy of any proposed publication at least thirty (30) days in advance of the date of submission for publication.
- Within said thirty (30) day period, Grifols shall:
  - Review such proposed publication for Confidential Information (other than Study results) and for subject information subject to the Health Insurance Portability and Accountability Act of 1996 ("HIPAA") and other applicable privacy laws;
  - Review such proposed publication for the unauthorized use of the name, symbols and/or trademarks of Grifols;
  - By written notice to the Investigator, identify with specificity the text or graphics in such proposed publication that Grifols contends contains Confidential Information, protected subject information or the unauthorized use of Grifols' name, symbols and/or trademarks so that the proposed publication may be edited appropriately to remove such text or graphics before publication; and

- By written request, Grifols may delay proposed publications up to sixty (60) days to allow Grifols to protect its interests in Grifols Inventions described in such publications.
- Institution and/or Investigator shall give Grifols the option of receiving an acknowledgment for its sponsorship of the study in all such publications or presentation.

## **10 APPENDICES**

## Appendix 1      Schedule of Study Procedures

Visit Type	Baseline Visit		Study Visit	Study Visit	Study Visit	Final Study /Early Discontinuation Visit
Study Day	Day 0	Day 1	Day 7 a	Day 14 a	Day 21 a	Day 28 a
Informed Consent	X					
Subject Number Assigned	X					
Inclusion/Exclusion Criteria	X					
Medical History b	X					
Physical Exam c	X					X
Height	X					
Weight d	X					
Vital Signs e	X	X	X	X	X	X
Viral NAT/Serology	X k, n					X n
Urine Pregnancy Test f	X					X
Biochemistry and Hematology	X k					X
Thromboembolic events risk monitoring	X k	X m	X			X
Hemolysis assessment g	X k	X m	X			X
Biomarker Retains ( only for subjects who provide consent for this portion of the study )	X k		X	X	X	X
AChR (or MuSK) Antibody testing (See Section 3.7.3.4 for details)	X k			X		X
QMG scale	X k		X	X	X	X
MG-Composite Scale	X k		X	X	X	X
MG-ADL	X		X	X	X	X
IgG levels	X k	X l	X	X	X	X
Preparation/Dispensing of IP h	X	X				
IP Infusion i	X j	X				
AE Assessment	X	X	X	X	X	X
Concomitant Medications	X	X	X	X	X	X

[figure not shown]
Note: Each MG assessment should be performed by the same clinical staff member whenever possible.

- a A ± 1 day window is allowed for Study Visits at Days 7 and 14. A ± 2 day window is allowed for study visits at Days 21 and 28
- b Includes demographics and concomitant diseases
- c Excludes breast and genitourinary exam
- d The recorded weight will be used to calculate the IP infusion dose at the Baseline (Day 0, Day 1) Visit
- e Vitals signs will be monitored per standard site/caregiver procedures; any clinically significant vital sign will be recorded as an AE in the eCRF
- f Potential child-bearing females only; results must be negative for subject to continue in the study
- g Local laboratory is to be utilized for testing and reporting. If the local laboratory is unable to perform any of the assessments, the central laboratory may be utilized.
- h To be performed by a pharmacist, or designee, per the Pharmacy Manual
- i Documentation of total infusion volume prepared (as received from pharmacist or designee), total time to infuse, total volume infused, and, if necessary, any infusion interruption with explanation. Please refer to [Section 3.7.2.1](#) to review monitoring vital signs during the two consecutive infusions on Day 0 and Day 1
- j Inclusion/exclusion criteria must be satisfied before the subject receives the first IP infusion
- k Samples (or assessments) to be collected (or conducted) within 8 hours prior to IP infusion on Day 0
- l Sample to be collected 30 ± 10 minutes post-completion of the IP infusion on Day 1.
- m Samples (or assessments) to be collected (or conducted) between 8 and 24 hours post-completion of IP infusion on Day 1
- n Collect samples but test only if the subject exhibits clinical signs and symptoms consistent with hepatitis A, hepatitis B, hepatitis C, HIV, or parvovirus B19 infection while participating in the study; These samples will be retained until all analyses in support of the study are complete; see [Table 3-1](#).

[figure not shown]
## Appendix 2 MGFA Clinical Classification

Classification	Description
Class I	Any ocular muscle weakness; may have weakness of eye closure. All other muscle strength
Class II	Mild weakness affecting muscles other than ocular muscles; may also have ocular muscle weakness of any severity
IIa	Predominantly affecting limb, axial muscles, or both. May also have lesser involvement of oropharyngeal muscles
IIb	Predominantly affecting oropharyngeal, respiratory muscles, or both. May also have lesser or equal involvement of limb, axial muscles, or both
Class III	Moderate weakness affecting muscles other than ocular muscles; may also have ocular muscle weakness of any severity
IIIa	Predominantly affecting limb, axial muscles, or both. May also have lesser involvement of oropharyngeal muscles
IIIb	Predominantly affecting oropharyngeal, respiratory muscles, or both. May also have lesser or equal involvement of limb, axial muscles, or both
Class IV	Severe weakness affecting muscles other than ocular muscles; may also have ocular muscle
IVa	Predominantly affecting limb, axial muscles, or both. May also have lesser involvement of oropharyngeal muscles
IVb	Predominantly affecting oropharyngeal, respiratory muscles, or both. May also have lesser or equal involvement of limb, axial muscles, or both
Class V	Defined as intubation, with or without mechanical ventilation, except when employed during routine postoperative management. The use of a feeding tube without intubation places the patient in class IVb

[figure not shown]
**Appendix 3        QMG Test Items**

**Appendix 4 MG Composite Scale**

**Appendix 5 MG Activities of Daily Living (MG-ADL) Profile**

## Appendix 6 Monitoring of Thromboembolic Events Risk

Subjects will be monitored for signs and symptoms of arterial and venous thromboembolic (TE) events. Arterial and venous TE events will be identified according to definitions in the International Classification of Diseases (ICD) [35]. Such events include, but are not limited to, deep vein thrombosis (DVT), pulmonary embolism (PE), acute myocardial infarction, cerebral infarction, acute ischemic heart disease, embolism or thrombosis of arteries of lower extremities, sagittal sinus thrombosis, portal vein thrombosis and injury of mesenteric artery.

All TE events will be recorded as adverse events (AEs) and reported accordingly. Any TE event fulfilling any of the criteria for “serious” will be reported as a serious adverse event (SAE).

The Sponsor’s Medical Monitor (or designee) will routinely review reported AEs for possible TE events.

Thromboembolic events risk will be determined by the Investigator or appropriate study staff as indicated by the following schedule (Table 1):

**Table 1. Schedule of Monitoring of Thromboembolic Events Risk**

Study visit	Wells score	D-dimer	Signs & symptoms of DVT and PE*
Day 0 (prior IP infusion)	X	X (within 8 hours prior IP infusion)	X
Day 1 (post-completion IP infusion)	X	X (between 8 and 24 hours post-completion of IP infusion)	X
Day 7 ( $\pm 1$ day)	X	X	X
Day 28 ( $\pm 2$ days)	X	X	X

\* Evaluation of clinical signs and symptoms of arterial and venous TE as part of AEs assessment.

Monitoring of thromboembolic events risk may be performed later, once laboratory results are available, blood collection for the D-dimer testing as well as the Wells score and evaluation signs and symptoms of DVT and PE must be performed as stated in the schedule of procedures.

Thromboembolic events risk will be determined using the **following** assessments:

[figure not shown]
1. The Wells Score [36] will be utilized to assess the clinical characteristics indicative of possible DVT or PE (Table 2);
2. Measurement of D-dimer blood levels [37];
3. Evaluation of clinical signs and symptoms of arterial and venous TE as part of AEs assessment.

**Table 2. Schedule of Monitoring of Thromboembolic Events Risk**

DEEP VEIN THROMBOSIS	
Clinical Characteristic	Score
Active cancer (treatment ongoing, within previous 6 months or palliative)	1
Paralysis, paresis, or recent plaster immobilization of the lower extremities	1
Recently bedridden >3 days or major surgery within previous 12 weeks requiring general or regional anesthesia	1
Previously documented DVT	1
Localized tenderness along distribution of deep venous system	1
Entire leg swollen	1
Calf Swelling 3 cm larger than asymptomatic side (measured 10 cm below tibial tuberosity)	1
Pitting edema confined to the symptomatic leg	1
Collateral superficial veins (non-varicose)	1
Alternative diagnosis at least as likely as DVT	-2
Total Score:	
PULMONARY EMBOLISM	
Clinical Characteristic	Score
Previous DVT or PE	1.5
Surgery or bedridden for 3 days during past 4 weeks	1.5
Active cancer (treatment within 6 months or palliative)	1
Hemoptysis	1
Heart rate > 100 beats/min	1.5
Clinical signs of DVT	3
Alternative diagnosis less likely than PE	3
Total Score:	

[figure not shown]
Thromboembolic events risk will be assessed according to the following algorithm adapted from Wells [36] (Figure 1 and Figure 2):

**Figure 1. Algorithm to Assess Thromboembolic Events Risk for DVT**

Any subject with a total Wells prediction score  $>1$  for DVT assessment should have further diagnostic testing per study site standard of care to confirm the occurrence of a TE (Figure 1).

Any subject with a total Wells prediction score  $\leq 1$  for DVT assessment and a positive D-dimer value (i.e., above Baseline and out of normal range of the reporting laboratory) in combination with clinical signs or symptoms of a TE (as per AEs assessment and such as pain, dyspnea, discoloration -paleness or redness- in lower extremities) should have further diagnostic testing per study site standard of care to confirm the occurrence of a TE (Figure 1).

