### 3.6.1 Thromboembolic Events Risk

During the clinical trial, TE risk will be determined by the Investigator or study staff using the measurement of D-dimer blood levels, the Wells clinical prediction rule for both DVT and for pulmonary embolism (PE), and evaluation of clinical signs and symptoms of TEs (such as pain, dyspnea, discoloration -paleness or redness- in lower extremities). Monitoring will be performed at Day 0 (prior infusion), Day 1 (after the infusion), Day  $7 \pm 1$  and Day  $28 \pm 2$ .

Procedures for the monitoring of TEs risk are provided in [Appendix 6](#).

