#### During and Post-completion of the IP infusion (Day 0)

- Pharmacist, or designee, to prepare and dispense the IP per Pharmacy Manual
- Administer the infusion (Per Pharmacy Manual)
- During the infusion, vital signs (including T, RR, HR, SBP, and DBP) will be monitored and recorded 1) within  $15 \pm 5$  minutes before the beginning of each infusion; 2) every  $30 \pm 10$  minutes during the first hour of each infusion; and 3) at  $30 \pm 10$  minutes post-completion of each infusion. **Note:** Any clinically significant vital sign will be recorded as an AE in the eCRF.
- Documentation of total infusion volume prepared (as received from pharmacist or designee), total time to infuse, total volume infused, and, if necessary, any infusion interruption with explanation
- AE, concomitant medication

## STUDY VISIT AT DAY 1

- Pharmacist, or designee, to prepare and dispense the IP per Pharmacy Manual
- Administer the infusion (Per Pharmacy Manual)
- During the infusion, vital signs (including T, RR, HR, SBP, and DBP) will be monitored and recorded 1) within  $15 \pm 5$  minutes before the beginning of each infusion; 2) every  $30 \pm 10$  minutes during the first hour of each infusion; and 3) at  $30 \pm 10$  minutes post-completion of each infusion. **Note:** Any clinically significant vital sign will be recorded as an AE in the eCRF.
- Laboratory assessments (see [Section 3.7.3](#)):
  - Urine collection (**between 8 and 24 hours post-completion of the IP infusion on Day 1**)
    - Hemolysis (urine sediment and measuring of hemoglobinuria). Note: Local laboratory is to be utilized for testing and reporting. If the local laboratory is unable to perform any of the assessments, the central laboratory may be utilized.
  - Blood collection (**at 30 minutes post-completion of the IP infusion on Day 1**)
    - IgG levels
  - Blood collection (**between 8 and 24 hours post-completion of the IP infusion on Day 1**)
    - D-dimer
    - Hemolysis (whole blood hemoglobin, serum or plasma free hemoglobin, haptoglobin, LDH, DAT, ARC, RBC, hematocrit, TBL, indirect bilirubin, and blood smear). Note: Local laboratory is to be utilized for testing and reporting. If the local laboratory is unable to perform any of the assessments, the central laboratory may be utilized.
- Thromboembolic events risk monitoring ([Appendix 6](#)) (**post-completion of the IP infusion on Day 1**)

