## 3.9 Removal of Subjects

Subjects may withdraw or be withdrawn from the study for the following reasons:

1. At their own request or at the request of their legally acceptable representative.
2. If, in the Investigator's opinion, continuation in the study would be detrimental to the subject's well-being.
3. At the specific request of the Sponsor.

Also, subjects must be withdrawn for the following reasons:

- Subjects not meeting the inclusion and exclusion criteria prior to the Baseline (Day 0) Visit based on local laboratory results
- Subjects with an occurrence of a concomitant disease or any medical condition which, either because of its severity or duration or necessary change in treatment, contravenes the condition of the study or puts the patient at unnecessary risk or harm
- Subjects with an occurrence of an AE which in the opinion of the Investigator and/or subject requires termination of treatment
- Subjects who are noncompliant with the protocol per the Investigator's discretion
- Pregnancy

In all cases, the reason for withdrawal must be recorded in the eCRF and in the subject's records.

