### 4.4 Procedures for Eliciting Reports of and for Recording and Reporting Adverse Events and Intercurrent Illnesses

#### 4.4.1 Adverse Event

An AE is defined as any untoward medical occurrence in a patient or clinical investigation subject administered a medicinal product or study treatment and which does not necessarily have a causal relationship with this administration. An AE can therefore be any unfavorable and unintended sign (including any abnormal laboratory finding, for example), symptom or disease temporally associated with the use of a medicinal product, whether or not considered related to the medicinal product.

Any AE that occurs at any time between signature of the ICF and last day of the subject's participation in the clinical trial must be reported and recorded on the AE eCRF entry. However, MG exacerbations defined as inclusion criteria will not be considered an AE.

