5.1 Data Handling

Unless otherwise noted, if an observation is missing at a specific scheduled visit/time point, the value at that visit/time point will not be imputed and will be set to missing.

Baseline in general will be defined as the last non-missing measurement taken prior to the start of the study drug infusion.

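### As worded below Figures 1 and 2 of Appendix 6, a positive D-dimer cannot occur on Day 0, so an abnormal pre-dose value in a symptomatic subject with low Wells scores directs no testing

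*Protocol*

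**What the plan says.** Protocol 3.6.1 makes TE risk a scheduled determination from D-dimer, the Wells rules and clinical signs: "Monitoring will be performed at Day 0 (prior infusion), Day 1 (after the infusion", then Day 7 and Day 28. Section 3.7.2.1 repeats the Appendix 6 assessment among the procedures before the Day 0 infusion. Table 1 of Appendix 6 marks all three components at each of the four visits.

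The text below Figure 1 directs further testing when the DVT Wells score exceeds 1. At 1 or below, it asks for signs or symptoms of a TE together with "a positive D-dimer value (i.e., above Baseline and out of normal range of the reporting laboratory". The text below Figure 2 uses the same definition at a PE Wells score of 4 or below, without a symptom condition. Neither paragraph is restricted to particular visits.

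Appendix 6 does not define Baseline. SAP 5.1 does: "Baseline in general will be defined as the last non-missing measurement taken prior to the start of the study drug infusion".

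The second D-dimer is drawn "between 8 and 24 hours post-completion of the IP infusion on Day 1" (Protocol 3.7.2.1, Study Visit at Day 1). The two 1 g/kg infusions are given on Day 0 and Day 1 (3.3.3.3). On when the assessment is made, Appendix 6 adds below Table 1: "Monitoring of thromboembolic events risk may be performed later, once laboratory results are available".

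**The concern.** The plan runs a safety rule on Day 0, but one branch of it has a single possible result there. A subject may have symptoms that suggest a thrombosis, score at or below both Wells cut-offs, and have a clearly abnormal D-dimer before dosing. The algorithm then directs no testing. The value is not used until it becomes the comparator for a sample taken after the whole dose.

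The practical stake is the second 1 g/kg. D-dimer is a local test (Table 3-1), so a result could be in hand before the Day 1 infusion. Section 3.9 requires withdrawal for a medical condition that "contravenes the condition of the study or puts the patient at unnecessary risk or harm". A prompt to investigate between the infusions would therefore have somewhere to lead.

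**Working it through.** The plan states no figure to reproduce here. The check is one of logic, schedule and Wells arithmetic.

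**1. The Day 0 rule.** Let D be the visit value, B the Baseline value and U the laboratory's upper limit. A positive result is (D > B) and (D > U). On Day 0, D = B, so D > B is false however far D lies above U.

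**2. Dose given by each scheduled D-dimer** (Appendix 6 Table 1; Protocol 3.3.3.3).

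| Sample | Dose already given | Can it exceed Baseline? |
|---|---|---|
| Day 0, within 8 h before infusion | 0 g/kg | No, it is Baseline |
| Day 1, 8 to 24 h after infusion ends | 1 + 1 = 2 g/kg | Yes, first opportunity |
| Day 7 | 2 g/kg | Yes |
| Day 28 | 2 g/kg | Yes |

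The branch can first be positive on a scheduled sample after 2 of 2 g/kg. If an out-of-range Day 0 value were evaluated before the Day 1 infusion, that would be 1 of 2 g/kg. A subject who stopped after the first infusion would have received 1 g/kg. An unscheduled D-dimer between infusions could qualify earlier.

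**3. Can a symptomatic subject stay at or below both cut-offs?** In Appendix 6 Table 2 the largest single item is 1 for DVT and 3 for PE. Anyone credited with at most one item on each list scores DVT ≤1 and PE ≤3, below the point where the Wells score alone directs testing.

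- *Example 1:* a painful red leg, not bedridden, heart rate ≤100. Leg pain and redness are symptoms named in the Figure 1 text but are not Table 2 items. DVT is 0, or 1 with deep-vein tenderness. PE is 0, or 3 with clinical signs of DVT. No testing is directed on Day 0 at any D-dimer. The example fails with a second DVT item (1 + 1 = 2 > 1), or with clinical signs of DVT plus heart rate >100 (3 + 1.5 = 4.5 > 4).
- *Example 2:* bedridden more than 3 days, heart rate >100, hemoptysis. DVT is 1; PE is 1.5 + 1.5 + 1 = 4.0, which is not above 4. This holds only if "Alternative diagnosis less likely than PE" is not credited. With it, PE is 4.0 + 3 = 7.0 and testing follows.

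**4. The symptom condition on Day 0.** The Figure 1 text ties TE symptoms to the adverse event assessment. Sections 4.3.1 and 4.4.1 start adverse event recording at consent, and consent is itself a Day 0 procedure. Read literally, leg pain already present at consent is left out, and that is Example 1. In the other direction, 4.4.1 says: "However, MG exacerbations defined as inclusion criteria will not be considered an AE". Dyspnea, another symptom named in the Figure 1 text, should therefore not count when the exacerbation explains it. A Day 0 rule needs its own symptom wording on both points.

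**The case against.** **Day 0 is meant as a reference.** A change criterion needs a comparator, and a pre-dose sample cannot show a change. Appendix 7 has the same feature: it schedules a hemolysis assessment on Day 0, although its hemoglobin drop is measured from the preceding blood test. It stands that Day 0 is a sound comparator for Days 1, 7 and 28. But Appendix 7 spells out its intervals and defines a reaction to IGIV, which cannot precede dosing. Appendix 6 assesses TE risk, a meaningful question before dosing, and does not say that Day 0 is for reference only. Its Wells >1 and >4 branches do work on Day 0.

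**Suspected thrombosis is already screened before the first dose.** This largely stands. Wells >1 or >4 directs testing whatever the D-dimer. The visit includes a physical examination. Exclusion 12 covers embolism, 13 a known hypercoagulable state and 18 any condition making participation unadvisable. Results and assessments bearing on eligibility must be available before infusion. Nothing stops an investigator acting on a high Day 0 value. A reader might infer that subjects with a suspected thrombosis are dosed without any safeguard; these provisions rule that out.

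**The text may not be the whole rule.** Figures 1 and 2 are not shown and could contain a Day 0 branch. The SAP definition of Baseline is a general one for data handling, although the protocol's own habit of writing Baseline (Day 0) agrees with it. Both limits stand.

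**The stake is narrow.** No frequency is given, the examples depend on which items are credited, and nothing shows that a work-up would finish before the Day 1 infusion or stop it. This stands and keeps the point small.

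**Conclusion.** The point holds as a minor safety gap, worth considering, with moderate confidence. On the text below the figures, the D-dimer branch cannot be positive on Day 0. A symptomatic subject at or below both Wells cut-offs then has no algorithm-directed use of D-dimer until after 2 of 2 g/kg. This rests on three assumptions: Baseline in Appendix 6 means the Day 0 sample, the unseen figures add no Day 0 branch, and only scheduled samples count. The benefit of a change also assumes that the local result is back before the Day 1 infusion; the documents give no turnaround time.

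Two further readings are tempting and unsupported. One is that a work-up would have prevented the first infusion: no eligibility criterion uses D-dimer, and Appendix 6 lets the evaluation wait for laboratory results. The other is that the TE count or the efficacy results are compromised. All TEs are recorded as adverse events (4.3.5), SAP section 11 lists D-dimer and flags values outside the normal range, the efficacy analyses do not use D-dimer, and nothing in the documents allows an effect on the TE count to be derived.

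**What to change.** Add one Day 0 rule to Appendix 6, placed so that it covers both the DVT and the PE assessment:

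> The Day 0 D-dimer is the Baseline reference for Days 1, 7 and 28. On Day 0, a subject at or below the Wells cut-offs who has clinical signs or symptoms suggestive of a TE (including those already present at consent, and not explained by the qualifying MG exacerbation) and a D-dimer above the reporting laboratory's normal range is referred for further diagnostic testing under the site's standard of care. The evaluation is made as soon as the local result is available and, at the latest, before the Day 1 infusion.

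Keep the two-part definition of a positive D-dimer for Days 1, 7 and 28. Do not add a Day 0 trigger for asymptomatic subjects. The PE text has no symptom condition, so simply dropping the Baseline comparison there would send every subject with a raised Day 0 value for work-up.

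The Wells scores, local D-dimer and clinical signs are already collected on Day 0, so no new data and no SAP change are needed. The cost is a few extra standard-of-care work-ups and one result check before the second infusion. The rule does not guarantee a work-up before the first infusion.
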